3.7.2 General Methods

Continuous variables will be summarized using descriptive statistics (n, mean, standard deviation, median, and range). Categorical variables will be summarized using the count and proportion of patients in each category. Unless otherwise specified, all confidence intervals will be 2-sided and with a confidence level of 95%. Details of the data handling methods will be specified in the SAP. Unless otherwise specified, the week prior to randomization will be considered the baseline for efficacy analyses. For safety analyses, the baseline value is defined as the last non-missing value measured before administration of study treatment. All statistical analyses will be performed using SAS® Version 9.4 (or later) for Windows.

3.7.3 Patient Disposition, Demographics, and Baseline Characteristics

The count and proportion of patients included in the Randomized, Safety, and mITT Populations will be presented overall and by treatment group. The number of patients in the Screened Population will be presented overall.

The count and proportion of screen failures (ie, patients who enter the Screening Period but not the Pretreatment Period) and pretreatment failures (ie, patients who enter the Pretreatment Period but are not randomized), along with the associated reasons for failure, will be tabulated overall for the Screened Population.

The count and proportion of patients who complete the study and who prematurely discontinue will be presented for each treatment group and overall for the Randomized Population. The reason for premature discontinuation as recorded on the study completion forms of the eCRFs will be summarized by treatment group and overall for the Randomized Population.

Demographic parameters (eg, age, sex, race, weight, height, and body mass index) and other baseline characteristics (including heartburn severity, regurgitation frequency, and the weekly assessments) will be summarized by treatment group.

3.7.4 Efficacy Analyses

Table 4 and Table 5 provide the analysis time windows allowed for the efficacy analyses in the Pretreatment and Treatment Periods.

Table 4. Analysis Time Windows for Efficacy Analysis – Daily Assessments

Period	Analysis Week	Begins ^a	Ends ^a
Pretreatment (Baseline ^b)	Week -2	Day -14	Day -8
	Week -1	Day -7	Day -1 (Day before randomization)
Treatment	Week 1	Day 1 (Day of Randomization)	Day 7
	Week 2	Day 8	Day 14
	Week 3	Day 15	Day 21
	Week 4	Day 22	Day 28
	Week 5	Day 29	Day 35
	Week 6	Day 36	Day 42
	Week 7	Day 43	Day 49
	Week 8	Day 50	Day 56
	Week 9	Day 57	Day 63
	•••	•••	•••

a. Relative to the day of randomization (Day 1). There is no Day 0.

b. Baseline for efficacy parameters will be derived from the daily eDiary collected for Pretreatment Week -1 (Week -2 if data for Week -1 not available); specifically for the proportion endpoints (defined as days with the event of interest divided by the number of diary entry days), the last 14 days (Week -2 to Week -1) prior to day of randomization will be used.

Table 5.	Analysis Time Windows for Efficacy Analysis – Weekly Assessments
i abic 5.	Analysis I line windows for Efficacy Analysis – weekly Assessments

Period	Analysis Week	Begins ^a	Ends ^a
Pretreatment (Baseline ^b)	Week -2	Day -11	Day -5
	Week -1	Day -4	Day -1 (Day before randomization)
	Week 1	Day 7	Day 10
	Week 2	Day 11	Day 17
	Week 3	Day 18	Day 24
	Week 4	Day 25	Day 31
Treatment	Week 5	Day 32	Day 38
	Week 6	Day 39	Day 45
	Week 7	Day 46	Day 52
	Week 8	Day 53	Day 59
	Week 9	Day 60	Day 66
	•••	•••	•••

a. Relative to the day of randomization (Day 1). There is no Day 0.

3.7.4.1 Primary Efficacy Parameter

The primary efficacy parameter of the study is defined as the change from baseline at Week 8 in WHSS.

- The WHSS for a week is the average of the non-missing Daily Heartburn Severity Scores (DHSS) for that week. Rules for missingness of data will be prespecified in the SAP finalized before database lock.
- The DHSS for a day is the greater score of the 2 mRESQ items assessing heartburn severity ("Burning feeling behind the breastbone or in the center of the upper stomach" and "Pain behind the breastbone or in the center of the upper stomach") for that day. Where 1 of the 2 mRESQ heartburn severity items is missing for the day, the maximum will be the score of the remaining item; where both items are missing for the day, the DHSS will be missing.

b. Baseline for efficacy parameters will be derived from the eDiary collected for Pretreatment Week -1 (Week -2 if data for Week -1 not available)

3.7.4.2 Key Secondary Efficacy Parameters

There are 3 key secondary efficacy parameters. Hypothesis testing of these key secondary efficacy parameters (and the primary efficacy parameter) will be controlled for multiplicity.

- 1. Change from baseline at Week 8 in Weekly Regurgitation Frequency Score (WRFS)
 - The WRFS for a week is the average of the non-missing Daily Regurgitation Frequency Scores (DRFS) for that week. Rules for missingness of data will be prespecified in the SAP finalized before database lock.
 - The DRFS for a day is the greater score of the 2 mRESQ items assessing regurgitation frequency ("Regurgitation [liquid or food moving upwards toward your throat or mouth]" and "An acid or bitter taste in the mouth") for that day.
- 2. Overall Heartburn Responder: a patient who is a weekly heartburn responder for at least 4 weeks, including at least 1 of the last 2 weeks (Weeks 7 and 8), during the 8-week Treatment Period.
 - A weekly heartburn responder is a patient with a decrease from baseline of ≥ 45% in Weekly Heartburn Severity Score (WHSS).
 - Rules for missingness of data will be prespecified in the SAP finalized before database lock.
- 3. Proportion of heartburn-free days during the 8-week Treatment Period
 - Proportion of heartburn-free days is calculated as the number of heartburn-free (DHSS=0) days divided by the number of diary entry days.

3.7.4.3 Analysis Methods for Primary and Key Secondary Efficacy Parameters

For analysis of the primary efficacy and first key secondary efficacy parameters, continuous parameters (eg, change from baseline), descriptive statistics (patient number [n], mean, standard deviation, median, and range) will be presented for each treatment group. The IW-3718 group will be compared with the placebo group by employing a linear mixed-effects model for repeated measures (MMRM) framework with week (categorical), treatment group, week-by-treatment group and week-by-baseline value interactions, baseline esophagitis status (present vs. not present), and baseline WHSS (<3 vs. ≥3) as fixed-effect terms and baseline value as a covariate, with patient as a random effect. An unstructured covariance structure will be used. Least-squares mean (LSM) for each treatment group, LSM difference between the IW-3718 group and the

placebo group and a 95% confidence interval for the difference at Week 8, as well as the p-value for comparison versus placebo will be presented.

For analysis of responder parameters (ie, responder vs. non-responder), the counts and proportions of responders will be calculated for each treatment group. The proportions of responders between the IW-3718 group and the placebo group will be compared using a Cochran-Mantel-Haenszel (CMH) test controlling for baseline esophagitis status (erosive esophagitis vs. no erosive esophagitis) and baseline WHSS (<3 vs. ≥3). The CMH test is the primary analysis for responder parameters. The difference in the proportion of responders between the IW-3718 group and the placebo group, as well as the CMH estimate of the odds ratio (IW-3718 over placebo) and a 95% confidence interval for the odds ratio, will also be presented.

Time-dependent proportion parameters, defined as days the event of interest occurs, divided by the number of eDiary entry days within the 8-week Treatment Period (eg, proportion of heartburn-free-days), will be analyzed using a Poisson model which is appropriate for count data. The analysis includes the treatment, the baseline esophagitis status (present vs. not present), baseline WHSS (<3 vs. ≥3), covariate of baseline proportion of event-free days, with the eDiary entry days adjusted in the model. In the case of overdispersion, a negative binomial model instead of Poisson regression will be implemented. Model estimates in difference between the rates for IW-3718 and placebo groups will be calculated with corresponding 95% confidence interval and p-value associated with the comparisons to placebo .

3.7.4.4 Controlling Type-I Error

To maintain an overall type-I error rate of 0.05, the primary and 3 key secondary efficacy parameters will be tested sequentially according to the following order, each at a 2-sided significance level of 0.05.

Order	Parameter
1	Change from Baseline at Week 8 in WHSS (primary)
2	Change from Baseline at Week 8 in WRFS
3	Overall Heartburn Responder
4	Proportion of Heartburn-free Days during the 8-week Treatment Period

Testing of subsequent parameters will not be performed unless all previous parameters have been tested statistically significant ($p \le 0.05$).

3.7.4.5 Sensitivity Analysis of Primary Efficacy Parameter

For the primary parameter, change from baseline in WHSS at Week 8, a sensitivity analysis will be conducted; details will be provided in the SAP.

3.7.4.6 Handling of Missing Data

For the primary efficacy analysis, change from baseline at Week 8 in WHSS, no imputation will be performed on missing data. The WHSS will be computed as the average of daily scores for that week. Rules for the average calculation will be prespecified in the SAP finalized before database lock.

A pattern-mixture model with control-based pattern imputation will be implemented as a multiple imputation method to explore the effects of missing data on the primary efficacy parameter. The details of this approach will be provided in the SAP.

3.7.4.7 Exploratory Efficacy Parameters and Analysis Methods

Exploratory efficacy parameters will be explored outside of the formal testing procedures and not controlled for multiplicity.

Change or percent change for continuous parameters will be analyzed using the MMRM approach as described for the primary efficacy parameter, change from baseline at Week 8 in WHSS.

Categorical responder parameters will be analyzed using the CMH testing method as described for the key secondary efficacy analysis for Overall Heartburn Responder.

Time-dependent proportion parameters, defined as days the event of interest occurs, divided by the number of diary entry days within the 8-week Treatment Period (eg, proportion of heartburn-free-days), will be analyzed using a Poisson model which is appropriate for count data. The analysis is similar to that described for the key secondary efficacy analysis for the proportion of heartburn-free days during the 8-week Treatment Period.

The exploratory efficacy endpoints and proposed analysis methods are listed below:

Item No.	Exploratory Efficacy Endpoints	Analysis Methods
1.	Percent change from baseline at Week 8 in WHSS	MMRM for change from baseline at Week 8.
2.	Overall Heartburn Responders with baseline WHSS ≥3	СМН
3.	Change from baseline in proportion of days when heartburn did not occur (DHSS = 0) or was very mild (DHSS = 1) during the 8-week Treatment Period	Analysis of covariance (ANCOVA)
4.	Proportion of days when heartburn did not occur (DHSS=0) or was very mild (DHSS=1) during the 8-week Treatment Period	Poisson regression for proportions
5.	Percent change from baseline at Week 8 in WRFS	MMRM for change from baseline at Week 8.
6.	Change from baseline in proportion of days when regurgitation did not occur (DRFS = 0) or rarely occurred (DRFS = 1) during the 8-week Treatment Period	ANCOVA
7.	Proportion of regurgitation free (DRFS = 0) days during the 8-week Treatment Period	Poisson regression for proportions
8.	Proportion of days when regurgitation did not occur (DRFS=0) or rarely occurred (DRFS=1) during the 8-week Treatment Period	Poisson regression for proportions
9.	 Overall Regurgitation Responder: a patient who is a Weekly Regurgitation Responder for at least 4 weeks, including at least 1 of the last 2 weeks (Weeks 7 and 8), during the 8-week Treatment Period A Weekly Regurgitation Responder is a patient with a decrease of ≥ 45% from baseline in WRFS A patient who reports DRFS for less than 4 days during a week will not be considered a Weekly Regurgitation Responder for that week 	СМН
10.	Change from baseline at Week 8 in each mRESQ item	MMRM for change from baseline at Week 8.
11.	Proportion of nights with difficulty falling asleep due to GERD during the 8-week Treatment Period	Poisson regression for proportions
12.	Proportion of days with nighttime awakening (≥1 time) due to GERD during the 8-week Treatment Period	Poisson regression for proportions
13.	Degree of relief of heartburn/regurgitation/overall GERD symptoms responder: • Degree of relief responder: patient who reported a score of 1-Significantly Relieved or 2-Moderately Relieved on the Degree of Relief question for at least 4 weeks, including at least 1 of the last 2 weeks (Weeks 7 and 8), during the 8-week Treatment Period	СМН
14.	Change from baseline at Week 8 in heartburn/regurgitation/overall GERD symptoms bothersomeness	MMRM for change from baseline at Week 8.
15.	Proportion of days with rescue medication use during the 8- week Treatment Period	Poisson regression for proportions

Item No.	Exploratory Efficacy Endpoints	Analysis Methods
16.	Erosive esophagitis (EE) healed (not present) at Week 8	СМН
17.	Proportion of patients with erosive esophagitis (EE) improved by at least 1 grade at Week 8	СМН

Descriptive supportive summary for following variables will be generated for mITT population.

Item No.	Description of Summary
1.	Percent change from baseline in WHSS by week
2.	Percent change from baseline in WRFS by week
3.	Change from baseline in WHSS by week
4.	Change from baseline in WRFS by week
5.	Change from baseline in each mRESQ item by week
6.	Proportion of heartburn-free (DHSS=0) days by week
7.	Proportion of regurgitation-free (DRFS=0) days by week
8.	Proportion of days when heartburn did not occur (DHSS=0) or was very mild (DHSS=1) by week
9.	Proportion of days when regurgitation did not occur (DRFS=0) or rarely occurred (DRFS=1) by week
10.	Proportion of nights with difficulty falling asleep due to GERD by week
11.	Proportion of days with nighttime awakening (≥1 time) due to GERD by week
12.	Proportion of days with rescue medication use by week
13.	Degree of relief of heartburn/regurgitation/overall GERD symptoms by week
14.	Heartburn/regurgitation/overall GERD symptoms bothersomeness by week
15.	Treatment satisfaction by week
16.	Shift in erosive esophagitis (EE) grade from baseline at Week 8

3.7.5 Safety Analyses

All safety parameters will be analyzed with descriptive statistics. Safety analyses will be performed on the Safety Population. The safety parameters will include AEs, clinical laboratory evaluations, vital signs, ECGs, and physical examination. For each safety parameter, the last non-missing assessment made before the first dose of study drug will be used as the baseline for all analyses of that safety parameter.

3.7.5.1 Adverse Events

Adverse event verbatim terms will be coded using the most current version of Medical Dictionary for Regulatory Activities (MedDRA) available at the start of the study. An AE (classified by preferred term) will be considered a TEAE if the AE occurred after initial study medication administration and within 1 day of the last dose of study medication. The number and percentage of patients reporting TEAEs will be tabulated by system organ class (SOC), preferred term, and treatment group. The number and percentage of patients reporting severe TEAEs, study drug-related AEs, AEs leading to study drug discontinuation, and treatment-emergent SAEs will also be tabulated by SOC, preferred term, and treatment group. Listings will be provided for deaths (if any), SAEs, and AEs leading to study drug discontinuation.

If a patient has more than 1 TEAE coded to the same preferred term, the patient will be counted only once for that preferred term.

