3.5.1 Adverse Events

3.5.1.1 Definitions

Adverse Event

An AE is any untoward medical occurrence associated with the use of a drug in humans, whether or not considered drug-related.

An AE, therefore, can be any unfavorable and unintended sign (including an abnormal laboratory finding, for example), symptom, or disease temporally associated with the use of a medicinal product, whether or not considered related to the medicinal product.

Note: A procedure is not an AE, but the reason for a procedure may be an AE.

Serious Adverse Event

An AE is considered "serious" if, in the view of either the Investigator or Sponsor, it results in any of the following outcomes:

- Death
- Life-threatening experience: An AE is considered "life-threatening" if, in the view of either the Investigator or Sponsor, its occurrence places the patient or subject at immediate risk of death. It does not include an AE that, had occurred in a more severe form, might have caused death.
- Inpatient hospitalization or prolongation of existing hospitalization: AEs requiring hospital admissions that are less than 24 hours in duration do not meet this criterion. A

scheduled hospitalization for a preexisting condition that has not worsened during participation in the study does not meet this criterion. Preplanned hospitalizations for an elective medical/surgical procedure or routine check-ups do not meet this criterion.

- A persistent or significant disability/incapacity or substantial disruption of the ability to conduct normal life functions
- A congenital anomaly or birth defect
- Is considered an important medical event: Important medical events that may not result in death, be life-threatening, or require hospitalization may be considered serious when, based upon appropriate medical judgment, they may jeopardize the subject and may require medical or surgical intervention to prevent one of the outcomes listed in this definition. Examples of such medical events include allergic bronchospasm requiring intensive treatment in an emergency room or at home, blood dyscrasias or convulsions that do not result in inpatient hospitalization, or the development of drug dependency or drug abuse.

Treatment-emergent Adverse Event

A treatment-emergent AE (TEAE) is an event that emerges, or a preexisting event that worsens, any time after administration of the first dose of study drug (Day 1).

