5.5.1. Adverse Events

An AE is any untoward medical occurrence associated with the use of a drug in humans, whether or not considered drug related.

An AE, therefore, can be any unfavorable and unintended sign (including an abnormal laboratory finding, for example), symptom, or disease temporally associated with the use of a medicinal product, whether or not considered related to the medicinal product. A procedure is not an AE, but the reason for a procedure may be an AE.

A treatment-emergent adverse event (TEAE) is an event that emerges, or a preexisting event that worsens (with a new start date), any time after administration of the first dose of study drug during the treatment emergent period, which is defined as the date and time of the first treatment to the date and time on or ≤ 1 day of the last treatment. In fact, there is an Investigator assigned flag on the eCRF to indicate an TEAE. The Investigator will provide an assessment of the AE relationship to study drug and AE severity for each AE.

The AE assessment (interview) will be collected from the time the patient signed the informed consent until completion of the Follow-up Phone Call. At each trial visit, the investigator will inquire about the occurrence of AEs/SAEs since the last visit. In addition, certain laboratory abnormalities and changes in vital signs, physical examination findings, and 12-lead ECG parameters are considered AEs per protocol if the Investigator considers them clinically significant and/or they necessitate intervention. These abnormal findings will be captured on the AE page of the electronic case report form (eCRF).

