7.10.1. Adverse Events

AEs will be coded by system organ class and preferred term using the MedDRA dictionary, version 23.0 which contains the COVID-19 specific terms. An AE will be considered a treatment-emergent AE (TEAE) if the AE started after initial study drug administration and within 1 day of the last dose of study drug. In addition, an AE that started before initial study drug but worsened after the first dosing of the study drug is also considered a TEAE.

The number and percentage of patients reporting TEAEs in each treatment group will be tabulated:

- by system organ class (SOC) and preferred term (PT)
- by SOC, PT, and severity
- by SOC, PT, and relationship to study drug.

If a patient has more than one TEAE coded to the same PT, the patient will be counted only once for that PT by identifying those TEAEs with the highest severity and the closest relationship to study drug.

The incidence of the following TEAEs will be summarized by PT:

- Most frequent ($\geq 2\%$ of patients in any treatment group) TEAEs
- Treatment Emergent SAEs
- TEAEs leading to premature discontinuation of study drug.

All AE summary tables will be SOC sorted alphabetically and have PT within each SOC sorted by decreasing frequency for IW-3718 group.

A TEAE summary table with all the non-SAEs by SOC and PT will be generated to support the clinicaltrials.gov reporting purpose.

AE listings will be presented for all patients with AEs, screened patients with SAEs, patients with AEs leading to discontinuation, all SAEs (no matter it is treatment-emerge or not) and patients who died (if any), respectively.

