7.10.2. Clinical Laboratory Parameters

Descriptive statistics for clinical laboratory values (in SI units) and changes from the baseline values at each assessment time point will be presented by treatment group for each clinical laboratory parameter. All laboratory data will be listed. The clinical laboratory parameters are listed in Section 5.5.6.

For each clinical laboratory parameter, the number and percentage of patients with potentially clinically significant (PCS) postbaseline clinical laboratory values will be tabulated by treatment group for data collecting no more than 1 day after the last dose. The criteria for PCS laboratory values are described in Table 8. The percentages will be calculated relative to the number of patients with available non-PCS baseline values and at least 1 post-baseline assessment. The

potential numerator will be the total number of patients with available non-PCS baseline values and at least 1 post-baseline PCS value in the corresponding postbaseline period.

A supportive listing for patients with PCS postbaseline values will be provided, including the PID number, study center, baseline and postbaseline values for each visit, and a flag indicating the PCS laboratory values.

Parameter	SI Unit	Lower Limit	Higher Limit
CHEMISTRY	· ·		I
Albumin	g/L	<0.9 × LLN	>1.1 × ULN
Alanine aminotransferase	U/L	_	$\geq 3 \times ULN$
Alkaline phosphatase	U/L	_	$\geq 3 \times ULN$
Aspartate aminotransferase	U/L	_	$\geq 3 \times ULN$
Bicarbonate	mmol/L	<0.9 × LLN	>1.1 × ULN
Bilirubin, total	μmol/L	_	>1.5 × ULN
Calcium	mmol/L	<0.9 × LLN	>1.1 × ULN
Chloride	mmol/L	<0.9 × LLN	>1.1 × ULN
Cholesterol, total	mmol/L		>1.6 × ULN
Creatinine	μmol/L	_	>1.3 × ULN
Glucose	mmol/L	<0.8 × LLN	>1.4 × ULN
Magnesium	mmol/L	<0.9 × LLN	>1.1 × ULN
Phosphate	mmol/L	<0.9 × LLN	>1.1 × ULN
Potassium	mmol/L	<0.9 × LLN	>1.1 × ULN
Protein, total	g/L	<0.9 × LLN	>1.1 × ULN
Sodium	mmol/L	<0.9 × LLN	>1.1 × ULN
Urea nitrogen	mmol/L	_	>1.2 × ULN
Uric acid	µmol/L	<0.9 × LLN	>1.1 × ULN
HEMATOLOGY	· ·		
Basophils, absolute cell count	10 ⁹ /L	_	>3 × ULN
Eosinophils, absolute cell count	10 ⁹ /L		>3 × ULN
Hematocrit	Ratio	<0.9 × LLN	>1.1 × ULN

 Table 8:
 Criteria for Potentially Clinically Significant Laboratory Results

Parameter	SI Unit	Lower Limit	Higher Limit
Hemoglobin	g/L	<0.9 × LLN	>1.1 × ULN
Lymphocytes, absolute cell count	10 ⁹ /L	<0.8 × LLN	>1.5 × ULN
Mean corpuscular hemoglobin	Pg	_	>3 × ULN
Mean corpuscular hemoglobin concentration	g/L	_	>3 × ULN

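### Treatment-emergent AE is defined four different ways, and the 1-day post-dose limit keeps some collected safety data out of the TEAE and PCS counts

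*Protocol*

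**What the plan says.** TEAE is defined in four places.

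- Protocol 3.5.1.1: a TEAE "is an event that emerges, or a preexisting event that worsens, any time after administration of the first dose of study drug (Day 1". No end is given.
- Protocol 3.7.5.1: an AE qualifies "if the AE occurred after initial study medication administration and within 1 day of the last dose of study medication". Worsening of a pre-existing event is not mentioned.
- SAP 5.5.1: new events qualify, and worsened ones if they carry a new start date. The period is "the date and time of the first treatment to the date and time on or ≤ 1 day of the last treatment". The section then remarks that "there is an Investigator assigned flag on the eCRF to indicate an TEAE", with no rule for a case where flag and dates disagree.
- SAP 7.10.1: a new event qualifies "if the AE started after initial study drug administration and within 1 day of the last dose of study drug". A further sentence admits events present before dosing that worsened after it, with neither an end date nor a new-start-date condition.

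AEs are collected from consent until the Follow-up Phone Call (Protocol 3.5.1.2), which takes place 7 days after the EOT Visit (Protocol 3.6.3). Completers take their last dose on the morning of that visit (Protocol 3.4.6). Patients who leave early have the EOT assessments when they discontinue (Protocol 3.6.4); no maximum interval from the last dose is set.

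For laboratory data, SAP 7.10.2 says that the number and percentage of patients with PCS values "will be tabulated by treatment group for data collecting no more than 1 day after the last dose". SAP 7.10.3 (vital signs) and 7.10.4 (ECG) carry the same limit.

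**The concern.** A TEAE table should be reproducible from the plan. Here the four texts differ in the end of the window, the handling of worsened events and the source of the classification (derived dates or investigator flag). Two programmers could each follow the documents and deliver different counts.

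The 1-day end also sits awkwardly with the collection schedule. The trial gathers AEs for a week after treatment, but every AE incidence table named in SAP 7.10.1 is a TEAE table, and no post-treatment table is planned. For laboratory, vital-sign and ECG data, the same limit can exclude an early terminator's final value from the PCS counts, and those are patients whose final safety values are of particular interest.

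**Working it through.** The plan states no figure on this point, so there is none to reproduce. The check sets the definitions side by side and counts days.

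**1. Four definitions applied to the same events.** Take a completer with EOT Visit and last dose on Day 57.

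| Event | Protocol 3.5.1.1 | Protocol 3.7.5.1 | SAP 5.5.1 | SAP 7.10.1 |
|---|---|---|---|---|
| New nausea, Day 30 | TEAE | TEAE | TEAE | TEAE |
| Nausea present before Day 1, worse on Day 30, no new start date | TEAE | not addressed | not TEAE | TEAE |
| New nausea, Day 62 | TEAE | not TEAE | not TEAE | not TEAE |
| Nausea present before Day 1, worse on Day 62, new start date | TEAE | not TEAE | not TEAE | TEAE |

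Only the first row gives one answer. Read literally, SAP 7.10.1 counts a worsening on Day 62 but not a new event on the same day. The investigator flag could give yet another answer in any row.

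**2. Days outside the window.** Inputs: last dose on the EOT day; call at EOT + 7.

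- EOT on Day 57: post-treatment collection covers Days 58 to 64, which is 7 days. Day 58 is within 1 day of the last dose. Days 59 to 64 are not: 6 of 7, or 86%.
- EOT on Day 60 (the end of the +3-day visit window): Days 61 to 67. Day 61 is inside and Days 62 to 67 are outside: again 6 of 7.
- As a share of all days from first dose to the call, with EOT on Day 57: 57 + 7 = 64 days, and 6/64 = 9.4%.

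These are shares of calendar days, not of events. Under the date-and-time wording of SAP 5.5.1, the window would close during the morning of the day after EOT, so slightly earlier.

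**3. Early-termination values in the PCS tables.** For completers, the EOT values fall on the day of the last dose and are kept. For an early terminator, a value enters the PCS counts only if taken no more than 1 day after the last dose. By the Schedule of Evaluations:

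- ECGs are taken at Screening, Randomization and EOT, so the EOT or early-termination ECG is the only scheduled post-baseline one.
- Laboratory tests and vital signs are taken post-baseline at Week 4 and EOT, so a patient who stops before Week 4 has only the early-termination set.

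Patients with an early-termination visit = sample size × discontinuation rate. SAP Appendix 1 gives about 10% for the Phase 2b study; 5% to 20% is an assumed range. The SAP gives two sample sizes, 660 (section 4) and 550 (section 3.4 and Appendix 1).

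| N | 5% | 10% | 20% |
|---|---|---|---|
| 660 | 33 | 66 | 132 |
| 550 | 28 | 55 | 110 |

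These patients are at risk of exclusion; they are not a count of exclusions. The share seen more than 1 day after the last dose is not given.

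**4. Numerator and denominator.** For laboratory and ECG, SAP 7.10.2 and 7.10.4 define the denominator as patients with a non-PCS baseline and at least one post-baseline assessment, without restating the 1-day limit. A patient whose only post-baseline ECG is late can therefore count in the denominator but never in the numerator. If k of n denominator patients are in that position, the reported percentage is x/n where a matched one would be x/(n − k), so it is (1 − k/n) times the matched figure. The documents do not give k. For vital signs, SAP 7.10.3 ties the denominator to the corresponding post-baseline period, so this mismatch is confined to laboratory and ECG.

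**The case against.** The strongest reply is that a short on-treatment window is defensible here. Protocol 1.2 describes a drug that is not systemically absorbed, stays in the gut and is held in the stomach for up to about 9 hours. Safety analysis is descriptive. Three of the four texts agree on the 1-day end for new events; the outlier is a general definitions section, and Protocol 3.7 leaves analysis detail to the SAP. SAP 5.5.1 says that the flag exists, not that tables are built from it.

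Much of this stands. The choice of a 1-day window is a judgement, not an error, and it can remain. But neither document gives that rationale, and it would not settle the worsening rule or the standing of the flag.

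A reader might infer more than the documents support:

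- **That the late data are removed from the analysis.** They are not. SAP 7.10.1 lists all patients with AEs and all SAEs, treatment-emergent or not. By-visit laboratory, vital-sign and ECG summaries have no last-dose limit, SAP Appendix 2 adds an End of Treatment row, and all laboratory and vital-sign data are listed.
- **That late events are missing from every incidence table under any reading.** Protocol 3.7.5.1 tabulates drug-related AEs and AEs leading to discontinuation without the treatment-emergent qualifier, and the worsening clause in SAP 7.10.1 has no end.
- **That late reporting costs events in patients who stop because they feel unwell.** The rule turns on onset. An on-treatment event first mentioned at the follow-up call is still a TEAE, and an event that causes a patient to stop ordinarily begins before the last dose.
- **That TEAE rates are materially understated.** Nothing in the documents shows how many events start more than 1 day after the last dose.

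**Conclusion.** The inconsistency holds. The four texts differ on the end of the window, on worsened events and on the source of the classification, so the TEAE counts are not fixed by the plan. Under the 1-day rule, new-onset AEs on 6 of a completer's 7 post-treatment collection days are outside the TEAE incidence tables and appear in listings only.

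For laboratory, vital-sign and ECG data, the effect is limited to the PCS counts and to early terminators assessed more than 1 day after the last dose. At the Phase 2b discontinuation rate, 55 to 66 patients would be at risk, with an unknown share affected. The laboratory and ECG denominators as worded can lower the PCS percentage when such patients exist.

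The day counts assume that completers take their last dose on the EOT day and that the call comes exactly 7 days later. The patient counts assume that the Phase 2b rate carries over. Efficacy conclusions are not touched. The point should be corrected because reported safety counts depend on it and the correction is simple.

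**What to change.** - Use one date-derived TEAE definition in Protocol 3.5.1.1 and 3.7.5.1 and SAP 5.5.1 and 7.10.1, stating the start, the end and the same end for new and worsened events. Say that dates govern over the eCRF flag. Worsening then needs its own date in the data, since Protocol 3.5.1.4 asks for one start date with the maximum intensity of an event.
- The 1-day window may stay as the on-treatment table. Add an incidence table of AEs and SAEs with onset or worsening from first dose through the Follow-up Phone Call.
- In SAP 7.10.2 to 7.10.4, include all post-baseline values through the EOT or early-termination visit in the PCS tables, and define numerator and denominator over the same values.

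The cost is aligned wording, a changed date filter and one extra table set. Counts may be slightly higher in both arms.
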